8.2 XT-150 administration

XT-150 will be administered as a bolus intra-articular injection into the joint space of the knee.

8.3 Placebo administration

Stage A only: placebo (1 mL sterile phosphate-buffered saline for injection) will be administered as a bolus intra-articular injection in the joint space of the knee.

8.4 XT-150 Blinding

The Investigator, study staff, and participants will be blinded to the treatment administration. The unblinded pharmacy will provide ready-to-use syringes, coded by participant number to the clinical staff. The Pharmacy will maintain a log in a secure location with the participant number and the assigned lot number of the investigational product. Lot numbers are unique to dosage strengths.

8.5 Comparator

Sterile phosphate-buffered saline (PBS) will be used as the placebo comparator. Data from pilot studies in animals showed that saline solutions produce no efficacious benefit in a wide variety of pain models. PBS has not demonstrated clinical benefit for pain and is therefore suitable for use as a placebo.

8.6 Compliance

Treatment compliance for intra-articular study drugs will be documented in the CRF by recording the date, start time, stop time, and whether the dose of study drug was completely injected.

8.7 Previous and Concomitant Medications and Substances

All pain therapy (both medications and treatments) and all prescription and over-the-counter medications and supplements administered within the last month prior to enrollment will be documented in the CRF. Participants who received systemic treatment with a prohibited medication before enrolling may not receive study drug injection.

8.7.1 Prohibited medications

The following treatments are prohibited prior to study drug administration:

- Current treatment with antibiotics or antiviral agents, except as topical treatments.
- Current treatment with immunosuppressive agents
- Current treatment with anti-platelets or anticoagulants. Aspirin ≤325 mg/day is allowed
- Current use of systemic corticosteroids
- Alcohol or illicit drug abuse within 1 year before the screening visit

Concomitant medications for pain will be allowed at doses and frequencies prescribed prior to the study treatment. New medications or escalation of pre-study treatments will be captured on CRFs during the 360-day evaluation period.

8.7.2 Rescue Medications

Acetaminophen ($\leq 3,000 \text{ mg}$ in 24 hours) will be allowed as rescue medication.

8.8 Accountability Procedures

The pharmacy or study personnel are responsible for ensuring that all XT-150 study drug shipments, inventory, and use are recorded and accountability is maintained.

The Sponsor's site monitors will be responsible for checking drug accountability at the site. Inventory records must be readily available for inspection by regulatory authorities at any time. Each shipment of study drug will contain an acknowledgment of receipt section for site signature. Upon receipt of study drug, the pharmacy or study personnel will visually inspect the shipment and verify the number and condition of vials or capsules received. Refer to the Pharmacy Manual for additional information.

8.9 Study Drug Handling and Disposal

Upon completion of the study, termination of the study, or upon written authorization from the Sponsor, all unused and partially used study drug will be centrally destroyed. All records of disposal by a centralized destruction site will be maintained by the Sponsor.

9.0 STUDY PROCEDURES

Study procedures should be completed within the windows provided in the Schedule of Assessments and Procedures located in Table 1 (Stage A) and Table 2 (Stage B). However, if a participant is unable to attend a visit within the specified windows, the PI (or qualified designee) should discuss appropriate scheduling with the Medical Monitor (or appropriate designee).

A telephone call documenting safety and efficacy assessments may be used for participants unable to physically attend follow up visits due to COVID-19 infection or corona virus exposure concerns. Home services may be employed for blood collections.

Any nonscheduled procedures required for urgent evaluation of safety concerns take precedence over all routine scheduled procedures.

9.1 Screening

Unless otherwise indicated, screening assessments should be performed within 30 days of enrollment.

- Obtain signed informed consent prior to initiating any study-related assessments or procedures
- Obtain a complete medical history and risk factors (e.g., active malignancy, diabetes mellitus, immunosuppression, transplant recipient, trauma, dialysis) and Intensive Care Unit admission and discharge (if applicable)
- Kellgren-Lawrence grading (obtain a new radiograph if not done in 6 months prior to Screening (See Appendix 5: Kellgren-Lawrence Grading)
- Choice of Index Knee
 - o Meets radiographic criteria: Kellgren-Lawrence grade 2 or 3

- o WOMAC Pain Subscore ≥ 8
- o If bilateral OA and both knees meet the first 2 criteria, the participant and investigator will jointly identify which knee will receive study drug
- o Record Left or Right knee as the Index Knee
- Obtain history of all pain medications and all other medications (prescription and over-the-counter [OTC]) and supplements)
- Conduct FAST assessment
- Participant training on accurate pain reporting
- Clinical assessments
 - Conduct complete physical examination, including height and weight (calculate body mass index [BMI])
 - o Measure vital signs (temperature and the site collected [oral, rectal, temporal, or tympanic], heart rate, blood pressure, and respiratory rate)
 - o Verify WOMAC Pain Subscore ≥ 8 attributable to the Index Knee.
- Laboratory assessments
 - Obtain blood samples for:
 - Hematology tests (complete blood count [CBC] with differential and platelets count),
 - coagulation laboratory tests (prothrombin time [PT] / international normalized ratio [INR] and either partial thromboplastin time [PTT] or activated partial thromboplastin time [aPTT]),
 - HIV, Hepatitis B and C
 - Serum pregnancy test for women of child-bearing potential
 - Serum chemistry tests (Appendix 1)
- Confirm participant qualification by inclusion/exclusion criteria

9.2 Baseline

Baseline assessments may be completed the day before or day of study drug administration, before the XT-150 injection.

- Training for accurate pain reporting
- Brief physical exam, including examination of Index Knee
- Obtain any changes from the complete medical history.
- Record any changes or updates in medications, including pain medications and therapies administered since Screening visit.
- Efficacy assessments

- o Record Baseline BPI scores (Appendix 2)
- o Record Baseline KOOS (Appendix 3)
- OA in your knee affects you, how are you doing today?" on a scale of 1 to 5, 1 being very good (asymptomatic and no limitation of normal activities) to 5, very poor (very severe, intolerable symptoms and inability to carry out normal activities)
- o Record baseline non-prescription pain therapies or practices
- 0
- Clinical assessments
 - Measure vital signs (temperature and the site collected [oral, rectal, temporal, or tympanic], heart rate, blood pressure, and respiratory rate)
- Laboratory assessments
 - Obtain serum for analysis of anti-IL-10 antibodies
- Confirm participant qualification by inclusion/exclusion criteria. Enroll participant prior to dosing

9.3 Day 0

- Before administering study drug:
 - Confirm that all study criteria are met (inclusion and exclusion)
 - Brief physical exam
 - Injection site examination of the Index Knee
 - Record any ongoing medical observations that occurred since Screening visit
 - Record any new AEs since Screening
 - Record any concomitant medications since Screening including prescription, OTC, and herbal medications. Ensure no excluded medications.
- Administer study drug (Section 8.0 for details on preparation)
 - Aseptic techniques will be used in the preparation and administration of XT-150.
 - Injections to the knee space will be guided by ultrasound, fluoroscopy or equivalent visualization
 - All injections of study drug must be performed by a specialist who is qualified, trained, and experienced to perform intra-articular injections
 - Examine injection site for infections or reactions
- Clinical assessments

- Monitor Participant for signs of study drug reaction
- Measure vital signs (temperature, heart rate, blood pressure, and respiratory rate) at least once about 1 hour after injection
- Refresh training on accurate pain reporting

9.4 Between clinic visits:

9.5 Follow up Visits – Stage A

(Day 7 [±1 day], 30 [±2 Days], 60 [±7 Days], 90 [±7 Days], 120 (±7 days) and 150 (±7 days)

- Clinical assessments
 - o Brief physical exam, including the injection site for infections or inflammation
 - Measure vital signs (temperature, heart rate, blood pressure, and respiratory rate)
- Efficacy assessments
 - o Record BPI scores (Appendix 2)
 - Record KOOS scores (Appendix 3)
 - Record participant's response to the question: "Considering all the ways the OA in your knee affects you, how are you doing today?" on a scale of 1 to 5, 1 being very good (asymptomatic and no limitation of normal activities) to 5, very poor (very severe, intolerable symptoms and inability to carry out normal activities)
 - Record changes in drug regimens or pain therapy

- Laboratory assessments
 - Day 60: Obtain blood samples for hematology tests (complete blood count [CBC] with differential and platelets count), coagulation laboratory tests (prothrombin time [PT] / international normalized ratio [INR] and either partial thromboplastin time [PTT] or activated partial thromboplastin time [aPTT]), and serum chemistry tests (Appendix 1)
 - Days 7 (±1 day), 30 (±2 days) and 60 (±7 days): Obtain serum for analysis of anti-IL-10 antibodies

- Assess, identify, and record any AEs since last visit
- Record any changes in concomitant medications since screening visit including prescription, OTC, and herbal medications.
- Refresh training on accurate pain reporting

9.6 Follow up Visit – Stage A, Day 180 [±7 days)

- Clinical assessments
 - o Brief physical exam, including the injection site for infections or inflammation
 - o Measure vital signs (temperature, heart rate, blood pressure, and respiratory rate)
- Efficacy assessments
 - Record BPI scores (Appendix 2)
 - Record KOOS scores (Appendix 3)
 - O Record participant's response to the question: "Considering all the ways the OA in your knee affects you, how are you doing today?" on a scale of 1 to 5, 1 being very good (asymptomatic and no limitation of normal activities) to 5, very poor (very severe, intolerable symptoms and inability to carry out normal activities)
 - Record changes in drug regimens or pain therapy

- Laboratory assessments: Obtain serum for analysis of anti-IL-10 antibodies
- · Assess, identify, and record any AEs since last visit
- Record any changes in concomitant medications since screening visit including prescription, OTC, and herbal medications.
- Refresh training on accurate pain reporting

At participant's option, administer a second injection to the Index Knee after Day 180 efficacy and safety assessments have been recorded. The second injection will be XT-150 active drug, randomly assigned to be either 150 μg or 450 μg. Record reason provided by the participant for requesting the second injection.

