- f. Participant assessment will be recorded in response to the question: "Considering all the ways the OA in your knee affects you, how are you doing today?" on a scale of 1 to 5, 5 being worst
- i. Women of child-bearing potential
- Verify that the participant meets all study inclusion and exclusion criteria before enrollment as close to study drug dosing as
 possible.
- k. Participant will receive a single, 1-mL dose of study drug into the intra-articular space of the knee on Day 0. Participant may elect a second injection on Day 180 (enters Stage B) after efficacy assessments have been recorded.
- A telephone call documenting safety and efficacy assessments may be used for participants unable to physically attend follow
 up visits due to COVID-19 infection or corona virus exposure concerns

Table 2. Schedule of Assessments and Procedures - Stage B

Scheduled Event	Follow up Visit Day ^d							
	210	240	270	300	330	360		
	(±7)	(±7)	(±7)	(±7)	(±7)	(±7)		
KOOS/WOMAC	X	X	X	X	X	X		
BPI	X	X	X	X	X	X		
Patient response to OA question	X	X	X	X	X	X		
	X	X	X	X	X	X		
						X		
Brief physical examination	X	X	X	X	X	X		
Record height and weight, calculate BMI						X		
Vital signs	X	X	X	X	X	X		
Clinical exam of the treated joints	X	X	X	X	X	X		
Record AEs	X	X	X	X	X	X		
Record SAEs	X	X	X	X	X	X		
	X	X	X	X	X	X		
Record concomitant medications	X	X	X	X	X	X		
Serum for anti-IL-10 antibody assessments						X		
Serum pregnancy test ^b						X		
Administer study drug ^c	X	X	X	X	X			

Footnotes to Table 2

- b. Women of child-bearing potential
 c. Participants may elect for one (1) XT-150 IA injection into the Index Knee at any point during Stage B up to Day 330, inclusive. The XT-150 dose (150 μg or 450 μg) will be randomly assigned.
- d. A telephone call documenting safety and efficacy assessments may be used for participants unable to physically attend follow up visits due to COVID19 infection or corona virus exposure concerns

$\mathbf{T}A$	BLE OF CONTENTS	
PF	OTOCOL SYNOPSIS	3
TA	BLE OF CONTENTS	10
	ST OF ACRONYMS, ABBREVIATIONS AND DEFINITIONS (
	RMS	
	CKGROUND AND RATIONALE	
4.1	XT-150	
4.2		
4.3	1	
4.4		

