7.4.2 Early Discontinuation from Study Drug Administration

Since the study treatment consists of a single dose of XT-150, and the participants should qualify for treatment before enrollment, no participants are anticipated to need to discontinue study drug unless they develop an SAE or need for excluded medications in the 24 hours prior to dosing.

NOTE: The Medical Monitor should be contacted to discuss whether to continue with planned XT-150 dosing in the event that the participant situation changes significantly in the 24 hours prior to XT-150 injection such that participant safety is at risk.

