9.7 Follow up Visits – Stage B

(Days 210 [±7 day], 240 [±7 Days], 270 [±7 Days], 300 [±7 Days], 330 [±7 Days], and 360 [±7 Days])

- Clinical assessments
 - o Brief physical exam, including the injection site for infections or inflammation
 - Measure vital signs (temperature, heart rate, blood pressure, and respiratory rate)
- Efficacy assessments
 - Record BPI scores (Appendix 2)
 - Record KOOS scores (Appendix 3)
 - O Record participant's response to the question: "Considering all the ways the OA in your knee affects you, how are you doing today?" on a scale of 1 to 5, 1 being very good (asymptomatic and no limitation of normal activities) to 5, very poor (very severe, intolerable symptoms and inability to carry out normal activities)
 - Record changes in drug regimens or pain therapy
 - Obtain serum for analysis of anti-IL-10 antibodies (Day 360)
 - Obtain serum for pregnancy test (Day 360)
- Assess, identify, and record any AEs since last visit
- At participant's option, administer a second injection to the Index Knee. The second injection will be XT-150 active drug, randomly assigned to be either 150 μg or 450 μg. Record reason provided by the participant for requesting the second injection.
- Record any changes in concomitant medications including prescription, OTC, and herbal medications.

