10.8 Adverse Events of Special Interest

10.8.1 Localized Signs of Infection or Inflammation at the Injection Site

Events that, in the opinion of the Investigator, may represent localized signs of infection or inflammation at the XT-150 injection site (e.g., pain, erythema, swelling, pruritus, warmth, hematoma, induration) must be recorded as AEs on the CRF. In general, these events will be temporally related to the injection.

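### The Day 0 eligibility and excluded-medication checks and all post-injection steps are not carried over to the second injection, and no visit is tied to its date

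*Protocol*

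**What the plan says.** **Second injection.** At Day 180, Section 9.6 of the protocol says: "At participant's option, administer a second injection to the Index Knee after Day 180 efficacy and safety assessments have been recorded". At the Stage B visits, Section 9.7 says: "At participant's option, administer a second injection to the Index Knee". Table 2 footnote c sets the window: "Participants may elect for one (1) XT-150 IA injection into the Index Knee at any point during Stage B up to Day 330, inclusive". Table 1 footnote k also covers the Day 180 injection, but places it after the efficacy assessments only.

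**First injection.** Before dosing, Section 9.3 lists confirmation of all inclusion and exclusion criteria, a brief physical examination, an Index Knee site examination, and an adverse event and medication review that ends with "Ensure no excluded medications". After dosing it lists a site examination, monitoring for a reaction, and vital signs "at least once about 1 hour after injection". Section 9.5 schedules the next examination at Day 7 ±1.

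**General provisions.** Section 7.4.2 describes treatment as one dose. It calls for Medical Monitor contact "in the event that the participant situation changes significantly in the 24 hours prior to XT-150 injection". Section 8.7.1 lists treatments prohibited before study drug administration and does not limit the list to Day 0. Section 10.8.1 makes local infection or inflammation an event of special interest, to be recorded as an adverse event, and adds: "In general, these events will be temporally related to the injection".

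**SAP.** Section 8.2 summarises injection-site examinations by treatment and study timepoint. Section 5.5 assigns adverse events to the Stage A or Stage B dose by onset date and derives the time since the Stage B dose.

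**The concern.** Safety and tolerability are the primary objective, and Section 4.4.2 names minor injection-site reactions as the most common related event. The Stage B injection is the only repeat exposure in the trial for participants given active drug in Stage A. It goes into the same joint, months after the entry criteria were last confirmed.

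Two things are at stake:

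- **Protection.** If sites follow the text, no listed step asks whether the participant still qualifies, and none requires observation after the injection.
- **Interpretation.** The protocol expects local reactions to cluster around the injection. That period has a scheduled examination after dose 1 but not after dose 2. Side-by-side rates would mix any true difference with a difference in when people were examined.

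**Working it through.** The documents give no figure to reproduce. The check sets the procedures side by side and then works out the visit gaps.

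**Procedures listed**

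| Step | First injection (9.2, 9.3, 9.5) | Second, Day 180 (9.6) | Second, Stage B visit (9.7) |
|---|---|---|---|
| Entry criteria confirmed | Yes | Not listed | Not listed |
| Excluded-medication check | Yes | Changes recorded only | Changes recorded only, listed after the injection |
| Physical and site examination | Before dosing | Before injection | Listed, order not stated |
| Vital signs at the visit | At Baseline | Before injection | Listed, order not stated |
| Adverse event review | Before dosing | Before injection | Listed, order not stated |
| Site examination after injection | Yes | Not listed | Not listed |
| Reaction monitoring | Yes | Not listed | Not listed |
| Vital signs at about 1 hour | Yes | Not listed | Not listed |
| Next scheduled examination | Day 7 ±1 | Day 210 ±7 | Next monthly visit ±7 |

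**Gap to the next scheduled examination.** Inputs are the visit days and windows in Tables 1 and 2.

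- First injection: 7 − 1 = 6 to 7 + 1 = 8 days.
- Second injection at a visit: nominal gap 30 days; shortest = (next visit − 7) − (injection visit + 7); longest = (next visit + 7) − (injection visit − 7).
- Day 180 visit: (210 − 7) − (180 + 7) = 203 − 187 = 16 days, to (210 + 7) − (180 − 7) = 217 − 173 = 44 days. The Day 210 to 300 visits give the same 16 to 44.
- Day 330 visit: the cap at Day 330 rules out a later injection, so the shortest gap is 353 − 330 = 23 days. The longest is 367 − 323 = 44 days.

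A dose-2 reaction that has settled before day 16 therefore cannot be seen at the next scheduled examination. After dose 1 there are two early examinations, on Day 0 and at Days 6 to 8. An injection between visits, which footnote c appears to allow, would have a gap that nobody planned.

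**Time since the criteria were last confirmed.** Earliest: 180 − 7 = 173 days. Latest: 330 days. The look-back in Section 7.4.2 is 24 hours.

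**Follow-up after dose 2.** From 360 − 180 = 180 days and six visits, down to 360 − 330 = 30 days and one visit.

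**Can Section 9.3 simply be read as applying again?** Not literally. Exclusion 2 bars anyone who has previously received XT-150. Two of the three Stage A groups are active, so 2 × 90 = 180 of about 270 participants would fail it. The protocol has to say which criteria govern re-dosing.

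**The case against.** The strongest reply is that re-dosing is far from unguarded. Section 9.6 requires the efficacy and safety assessments to be recorded first, and the visit includes the site examination, vital signs, adverse events and medications. Tables 1 and 2 list an examination of the treated joints at every visit. Section 8.7.1 is not confined to Day 0. Section 7.4.1 lets the investigator withdraw a participant in that person's interest, and Sections 10.3 and 10.9 rely on medical judgment. The rules in Section 9.3 on injector qualification, asepsis and image guidance reasonably cover every injection. All of this stands. A reader might infer that none of the Day 0 checks applies, or that nothing would stop re-dosing after, say, a local infection; the documents do not support either reading.

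A reader might also infer that dose-2 reaction rates are biased downward. That is not shown. Local reactions are adverse events after either dose, time since the Stage B dose is derived, and the visible text specifies no formal comparison of dose-1 and dose-2 reactions. Under-ascertainment is plausible, because Section 10.5.1 keeps non-serious osteoarthritis events out of the adverse event record, and knee pain or swelling first assessed weeks later is easier to attribute to osteoarthritis. Neither its direction nor its size can be computed.

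The body of Section 9.4, on the time between clinic visits, is missing from the available text, and some table rows are blank. Contact between visits cannot be excluded. The telephone provision in Section 9.0 does not fill the gap, since it is limited to COVID-19 reasons.

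Finally, Section 5.0 frames the primary objective around a single dose, and Section 4.4.5 reports none of its listed IL-10 effects after earlier second injections. Those effects are systemic or haematological rather than local. The earlier repeat-dosing study planned for up to 24 people, only some of them re-injected in the same knee.

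**Conclusion.** The point holds in a limited form. The entry-criteria confirmation, the explicit excluded-medication check and every post-injection step are absent from Sections 9.6 and 9.7, and no visit is tied to the second injection. The next scheduled examination comes at a nominal 30 days (16 to 44) instead of 7 (6 to 8). This assumes that the injection is given at a study visit and that the missing text adds no earlier contact.

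This is more than thin detail, because the provisions disagree. Section 7.4.2 assumes one dose and looks back 24 hours, Table 1 footnote k and Section 9.6 differ on what must come before the Day 180 injection, and exclusion 2 prevents the Day 0 criteria from being carried forward as they stand. The number affected is at most 270 and depends on how many participants elect re-dosing. The effect on reaction rates is unknown.

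**What to change.** **Protocol.**

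- Reconcile Sections 7.4.2, 9.3, 9.6 and 9.7, Table 1 footnote k and Table 2 footnote c.
- State which of the existing Section 9.3 steps, before and after dosing, apply to the second injection, and in what order.
- State which entry criteria apply, dealing expressly with exclusion 2.
- Reconcile the early follow-up after the two injections, or give the reason for the difference. Whether and how to align it, and which changes should bar re-dosing, is for the sponsor and Medical Monitor.

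**SAP.** Tabulate injection-site reactions and examinations by time since each injection, in addition to study timepoint. The derived time since the Stage B dose already supports this for adverse events. Wherever dose-1 and dose-2 rates appear together, report the unequal examination schedule beside them.

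**Cost.** One protocol amendment, possibly some added observation time for existing site staff, and one extra table. The SAP addendum says it was written after database lock and unblinding, so for second injections already given only the tabulation and the disclosure remain available.
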